15.0 Risks to Subjects

The risks to the percutaneous closure arm participants would be complications and/or adverse events associated with the closure procedure, up to and including death, which is rare. Some of the more common adverse events would include a need for transfusion due to blood loss, hematoma at the catheter access site, thrombosis, and embolization of the implant. For the latter, embolization during the procedure may be possible to resolve using percutaneous re-capture of the embolized device. However, if this fails, emergent surgery may be required, which is an additional risk. For the conservative management group, the risks involve failure to improve clinical status, or a depreciation in clinical status due to increased shunting of deoxygenated blood into the primary circulation. Volume overload due to the shunt also frequently causes ventricular remodeling and distension, affecting cardiac performance.

16.0 Potential Benefits to Subjects

The potential benefits to the arm receiving percutaneous closure would be a reduction in risks to develop morbidities or additional complications associated with PDA, as well as reduction in supplemental oxygen or ventilator support. For the conservative management arm, the benefits would be not having an invasive procedure with its affiliated risks and/or complications.

17.0 Data Management and Confidentiality

Clinical data from Nationwide Children's Hospital will be kept on the secure and limited-access patient database, EPIC. Echocardiography scans and reports will be stored on a secure and limited-access database, EcholMS. Data that is collected for analysis from these two sources will be stored on secure, limited-access shared storage locations (R:) as Excel files. Only the study team ([name], [name], [name], [name]) will have access to the collected data files containing confidential information and protected health information. Should significant biostatistical analyses be required (unanticipated at this time), only limited data sets will be used for this purpose after identifying information is removed. Data storage for patients at the University of Tennessee Health Sciences Center will be via their secure electronic medical records and other databases. PHI will be removed from ECHO reports and data collected at each institution prior to sharing of data files, which will be restricted to limited data sets (see *Data Sharing Between External Entities*).

18.0 Provisions to Monitor the Data to Ensure the Safety of Subjects

No DSMB is planned as both options are considered standard of care at NCH and the University of Tennessee Health Sciences Center.

19.0 Provisions to Protect the Privacy Interests of Subjects

All protected health information and confidential information will be stored on password-protected, limited access databases and computer systems. Only personnel appropriately trained and listed as members of the study team will be permitted to access any data files assembled for this research. Only limited data sets will be shared between collaborating institutions (see *Data Sharing Between External Entities*).

20.0 Compensation for Research-Related Injury

There are no plans to compensate for research-related injury, as all procedures are considered standard-of-care at Nationwide Children's Hospital, with known risks being discussed in detail with the patient's parents prior to conducting any procedure. For patients at UTHSC, compensation (if any) will be according to institutional protocols.

21.0 Economic Burden to Subjects

As all procedures are considered standard-of-care, parents and/or their health insurance carrier are expected to absorb all costs associated with the patient's care during their hospital stay. Research-specific echocardiographic studies, however, that are not part of routine care (qualifying / screening ECHO) will be paid by the research team.

22.0 Consent Process

Informed consent will be obtained by [name] or [name], both cardiologists at Nationwide Children's Hospital and co-investigators for this study. Consent at The University of Tennessee Health Sciences Center will be obtained by [name] or a designated member of his team. Face-to-face contact will be the primary method to obtain informed consent; however, telephone consents will be allowed for cases in which an infant was transferred from an outside institution and the parents are otherwise unavailable. Both treatment arms (intervention vs. non-intervention) will be clearly defined, and the randomized nature of the study will be clearly defined, as will the risks for each study arm. The provision of "Rescue intervention" will also be presented, if deemed clinically necessary, for those that may qualify from the non-intervention arm of the study if randomized to this arm. As noted previously, parents will also have the option to consent to prospective data collection only, if they refuse to permit randomization to one treatment arm or the other.

23.0 Process to Document Consent in Writing

After appropriate consultation and sufficient time has been provided to allow the parent(s) to make an informed decision regarding the study, they will be asked to sign a written consent form. They will also be asked to indicated whether or not they will permit randomization to a

PIVOTAL Pilot Study

specific treatment arm. If they decline, the consent will only be to allow prospective data collection.

24.0 Settings

Nationwide Children's Hospital, Main Campus (Columbus, OH)

University of Tennessee Health Sciences Center (Memphis, TN)

25.0 Resources Available

Nationwide Children's Hospital and The University of Tennessee Health Sciences Center have all resources necessary for the conduct of this study, with an exceptional neonatal intensive care unit (NICU) with specialists trained in neonatal care, echocardiography technicians trained and skilled in neonatal cardiac studies, and a specialized catheterization laboratory suite for percutaneous procedures staffed by pediatric cardiologists, anesthesiologists, technicians, and nurses.

26.0 Multi-Site Research

This pilot study will enroll patients at Nationwide Children's Hospital Main Campus in Columbus, OH and The University of Tennessee Health Sciences Center in Memphis, TN.

27.0 Protected Health Information Recording

1.0 Indicate which subject identifiers will be recorded for this research.

- Name
- Complete Address
- Telephone or Fax Number
- Social Security Number (do not check if only used for ClinCard)
- Dates (treatment dates, birth date, date of death)
- Email address , IP address or url
- Medical Record Number or other account number
- Health Plan Beneficiary Identification Number
- Full face photographic images and/or any comparable images (x-rays)
- Account Numbers

- Certificate/License Numbers
- Vehicle Identifiers and Serial Numbers (e.g. VINs, License Plate Numbers)
- Device Identifiers and Serial Numbers
- Biometric identifiers, including finger and voice prints
- Other number, characteristic or code that could be used to identify an individual
- None (Complete De-identification Certification Form)

2.0 Check the appropriate category and attach the required form* on the Local Site Documents, #3. Other Documents, page of the application. (Choose one.)

- Patient Authorization will be obtained. (Include the appropriate HIPAA language (see Section 14 of consent template) in the consent form OR attach the [HRP-900, HIPAA AUTHORIZATION](#) form.)
- Protocol meets the criteria for waiver of authorization. (Attach the [HRP-901, WAIVER OF HIPAA AUTHORIZATION REQUEST](#) form.)
- Protocol is using de-identified information. (Attach the [HRP-902, DE-IDENTIFICATION CERTIFICATION](#) form.) (Checked "None" in 1.0 above)
- Protocol involves research on decedents. (Attach the [HRP-903, RESEARCH ON DECEDENTS REQUEST](#) form.)
- Protocol is using a limited data set and data use agreement. (Contact the Office of Technology Commercialization to initiate a Limited Data Use Agreement.)

***Find the HIPAA forms in the [IRB Website Library, Templates](#).**

Attach the appropriate HIPAA form on the “Local Site Documents, #3. Other Documents”, page of the application.

3.0 How long will identifying information on each participant be maintained?

Identifying information will be kept until all of the desired data related to all participating patients has been collected.

4.0 Describe any plans to code identifiable information collected about each participant.

Should specialist biostatistical analysis be required (unanticipated at this time), identifying information (names, MRNs) will be removed from files shared with the biostatisticians, and the patients will be coded as subject 1, 2, 3, etc. Only limited data sets will be exchanged in this manner (due to possible need for date/timing information). Files with the links to this information will be kept on the computers of the local study PIs ([name], Nationwide Children's Hospital; [name], University of Tennessee Health Sciences Center).

5.0 Check each box that describes steps that will be taken to safeguard the confidentiality of information collected for this research:

- Research records will be stored in a locked cabinet in a secure location
- Research records will be stored in a password-protected computer file
- The list linking the assigned code number to the individual subject will be maintained separately from the other research data
- Only certified research personnel will be given access to identifiable subject information

6.0 Describe the provisions included in the protocol to protect the privacy interests of subjects, where "privacy interests" refer to the interest of individuals in being left alone, limiting access to them, and limiting access to their information. (This is not the same provision to maintain the confidentiality of data.)

Patients and their parent(s) will be afforded privacy in accordance with NCH and UTHSC standards for care. Contact with the parent(s) will be required in order to obtain consent. They will be asked by consenting personnel if they are open to the idea of having their child participate in a research study. Further contact would only be if they were willing to consider it or for further discussion during the process. Those that refuse will no longer be approached. Follow up for those who are "thinking about it" or "considering it" will be limited, as well. Additional contact with the parent(s) will be required prior to the interventional procedure (for patients randomized to the percutaneous intervention arm), in order to obtain consent for said procedure. This will be done by a member of the interventional cardiology team.

PIVOTAL Pilot Study

The qualifying ECHO scan is a research-specific scan, separate from any that would otherwise be performed for clinical purposes, and is recognized as an additional instance in which contact with the infant occurs, but is necessary for the purposes of the study to ensure that appropriate inclusion criteria are met, and that exclusion criteria are not present. This would include findings of non-hemodynamically-significant PDA, for which intervention would not be warranted.

All data obtained through the study will be stored in either a locked file in the research office (paper consent forms) or stored on a secured shared drive accessible only by password-protected computer systems behind the NCH firewall. Similar data security practices are in place at UTHSC. Prior to sharing data, PHI will be removed from data sources at NCH and UTHSC. Generic “identifiers” will be used for each case (“1”, “2”, “3”) in place of names and/or MRNs. (see *Data Sharing Between External Entities*).

Confidential Health Information

1.0 Please mark all categories that reflect the nature of health information to be accessed and used as part of this research.

- Demographics (age, gender, educational level)
- Diagnosis
- Laboratory reports
- Radiology reports
- Discharge summaries
- Procedures/Treatments received
- Dates related to course of treatment (admission, surgery, discharge)
- Billing information
- Names of drugs and/or devices used as part of treatment
- Location of treatment
- Name of treatment provider
- Surgical reports
- Other information related to course of treatment
- None

2.0 Please discuss why it is necessary to access and review the health information noted in your response above.

Several of the items indicated will be used as qualifying criteria for the study. This includes age / gestational age, diagnosis, and radiology (echocardiography) reports which are used to

determine final eligibility to participate in the study (see Inclusion Criteria). Date information is used to track the age at the time either intervention is applied, and how long a PDA remains open (in the conservative management group). Procedural data, surgical / procedural reports, and the device names all appear on the cardiac catheterization reports, which will be accessed for procedural data in the percutaneous treatment group. “Other information” may include incidence of adverse events in the percutaneous arm patients, treatments for adverse events, and all affiliated complications and morbidities experienced by both groups during the hospital stay, as well as respiratory therapy, ventilatory support required, and level of supplemental oxygen required during the hospital stay.

3.0 Is the health information to be accessed and reviewed the minimal necessary to achieve the goals of this research? Yes No

4.0 Will it be necessary to record information of a sensitive nature? Yes No

5.0 Do you plan to obtain a federally-issued Certificate of Confidentiality as a means of protecting the confidentiality of the information collected? Yes No

Data Sharing Between External Entities

1.0 Will it be necessary to share human subjects' data with a colleague or another person or entity not associated with Nationwide Children's Hospital (Ohio State University employees are considered external entities). Yes No

- List the intended external recipient(s) (institutions/entities) of such data:
University of Tennessee Health Sciences Center

2.0 Will it be necessary to receive human subjects' data from a colleague or an entity not associated with Nationwide Children's Hospital (Ohio State University employees are considered external entities). Yes No

- List the intended external sender(s) (institutions/entities) of such data:
University of Tennessee Health Sciences Center

3.0 Check the type of data shared:

- a. De-identified:
- b. Limited Data Set

- List the specific PHI elements (see **Protected Health Information Recording**) to be shared:

Diagnoses, dates of studies, and findings, dates of catheter closure (if applicable), type of implant used (if applicable) and any device-related adverse events and treatments

PIVOTAL Pilot Study

received, dates and detail on ventilatory and supplemental oxygen support, dates and detail of medications used to treat PDA-related cardiopulmonary symptoms, discharge date.

- c. Identifiable data with consent
- List the specific PHI elements (see **Protected Health Information Recording**) that will be obtained:

4.0 Briefly describe the manner in which data will be shared/transmitted between sites (such as via REDCap, Dropbox, etc).

Limited data sets may be shared via secure exchange of password-protected Excel files.

PIVOTAL Pilot Study

Table 1: Clinical and echocardiographic criteria that will be used to define a “hemodynamically-significant patent ductus arteriosus” (HSPDA) for the purposes of this pilot study.

| | | CLINICAL | | ECHOCARDIOGRAPHIC | | | |
|---|--|--|-----------------|--|--|--|--|
| Non-HSPDA | Asymptomatic | Room air, no positive airway pressure | None | No PDA | | | |
| | Mild | 
 CPAP (NIPPV) $\text{FiO}_2 < 0.30$ OR Any nasal cannula (including high-flow nasal cannula) | Small | 
 <1.5 mm diameter DA flow $V_{max} > 2.5 \text{ m/s}$ LA:Ao ratio $< 1.5:1$ ($\text{LVEDD [cm]} < 1.2$)* LVO (ml/kg/min) < 250 | | | |
| | Moderate | 
 CPAP (NIPPV) $\text{FiO}_2 0.30-0.50^{**}$ | Moderate | 
 $\geq 1.5-3 \text{ mm diameter}$ DA flow $V_{max} 1.5-2.5 \text{ m/s}$ LA:Ao ratio ≥ 1.5 to $2:1$ ($\text{LVEDD [cm]} \geq 1.2-1.5$)* LVO (ml/kg/min) $\geq 250-430$ Decreased or absent end-diastolic flow in DA | | | |
| HSPDA | Severe | 
 CPAP (NIPPV) $\text{FiO}_2 > 0.50^{**}$ OR Mechanical ventilation (conventional or high frequency)** | Large: | 
 $\geq 3 \text{ mm diameter}$ DA flow $V_{max} \leq 1.5 \text{ m/s}$ LA:Ao ratio $> 2:1$ ($\text{LVEDD [cm]} \geq 1.5$)* LVO (ml/kg/min) ≥ 430 Reversed end-diastolic flow in the DA | | | |
| | 
*Infants with an atrial septal defect or ventricular septal defect might have altered LA:Ao dimensions, wherein LVEDD (left ventricular end diastolic dimension) will also be used to assess PDA characteristics
 | | | | | | |
| | 
**Composite risk of death or moderate or severe BPD must be $> 50\%$ (Laughon et al. Prediction of Bronchopulmonary Dysplasia by Postnatal Age in Extremely Premature Infants. Am J Respir Crit Care Med. 2011)
 | | | | | | |
| 
DA= Descending aorta; LVO= Left ventricular output will be calculated as follows: $[(\text{Velocity time integral}) \times (\text{Heart rate}) \times (\text{Aortic cross-sectional area})]$ indexed to body weight
 | | | | | | | |

Figure 1: PIVOTAL pilot trial flowsheet

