1.0 Study Summary

| | |
|--|---|
| Study Title: | PIVOTAL Pilot Study |
| Study Design: | Randomized + Prospective |
| Primary Objective | Collect preliminary data to be used for a large multi-site randomized study proposal |
| Secondary Objective | Provide insight into parental willingness for randomization regarding treatment interventions to be used |
| Research Intervention(s) / Investigational Agents | 1) Percutaneous (catheter-based) closure of patent ductus arteriosus [active intervention], 2) Conservative management of patent ductus arteriosus [non-intervention] 3) "Rescue" intervention (if medically necessary for conservative management group [rescue intervention]) |
| IND/IDE # | N/A |
| Study Population | Premature infants born at <28 weeks gestation with hemodynamically significant patent ductus arteriosus (PDA) at days of life 14 – 28. |
| Sample Size | 10 each for interventions 1) and 2) for a total of 20 enrolled at NCH. 20 additional infants will be enrolled at the collaborating institution (University of Tennessee Health Sciences Center) Unknown additional for non-randomized prospective data collection (see protocol narrative) |
| Study Duration for individual participants | From birth to hospital discharge. |
| Study Specific Abbreviations / Definitions | PDA ≡ patent ductus arteriosus; ECHO ≡ echocardiography; HSPDA ≡ hemodynamically-significant patent ductus arteriosus; NCH ≡ Nationwide Children's Hospital; UTHSC ≡ University of Tennessee Health Sciences Center |

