- Increase in $\text{FiO}_2 >20\%$ from baseline value for >24 hours in the absence of atelectasis or worsening interstitial lung disease
- OR

PIVOTAL Pilot Study

- Increase in baseline creatinine >30% *and* creatinine >1 mg/dL
- AND
- ≥3 large ECHO criteria
- ≥1 large ECHO criteria AND mitral regurgitation (annular dilatation of the valve)

RESCUE CRITERIA #2

- Moderate OR severe clinical criteria AND ≥1 criteria for large ECHO criteria
- AND
- mitral regurgitation (annular dilatation of the valve)

Data to be Collected: Clinical echocardiographic data for NCH-enrolled patients will be obtained from ECHO reports on the EchoIMS server. Research ECHO data will be stored initially on the secure Merge database. ECHO data and reports are currently scheduled to be moved to the secure Siemens Syngo system in July of 2019. Catheterization data (Percutaneous intervention arm) and information will be obtained from the reports found under the “Cardiology” tab in EPIC. All other data will be obtained from the patient’s electronic medical record. Data collected at UTHSC will similarly involve the patient’s electronic medical records, and ECHO data retrieved from local, secure databases, if not embedded within the medical records.

Demographics (Patient): Date of birth, Gender, Gestational age, Birth weight, Birth length, Weight and length at procedure (if applicable), Study arm assignment

Echocardiographic (ECHO): Date of ECHO study, Results of ECHO studies - including all cardiac and major blood vessel measurements and performance evaluations, PDA size, PDA flow direction (All clinical ECHO studies, as well as research-specific ECHO studies), and any ECHO contraindications for percutaneous closure

Procedural (Percutaneous closure arm): Date of procedure, Type of implant / device used, Number of implant attempts, Procedural complications, Time of procedure start, Time of procedure end, Medications and anesthetics administered, fluoroscopic data (contrast dose, timing), receipt of transfusion (if applicable), Post-operative complications (if applicable), All hemodynamic measurements obtained – including size and type of PDA per angiography, Any catheter-based finding that would contraindicate percutaneous closure (ex – previously

PIVOTAL Pilot Study

undiagnosed aortic coarctation or narrowing of the left pulmonary artery), Any adverse events reported

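### Table 1 defines DA only as descending aorta, which fits its two end-diastolic-flow rows but not its three peak-velocity rows, where the duct appears to be meant

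*Combined protocol and SAP*

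**What the plan says.** Table 1 grades the PDA as small, moderate or large on echocardiography. The abbreviations footnote beneath it reads "DA= Descending aorta", and no other definition of DA appears in the protocol. The Section 1.0 list gives "PDA ≡ patent ductus arteriosus" but has no entry for DA.

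DA appears in five rows of the table:

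- Three rows grade the Vmax of DA flow: above 2.5 m/s for small, 1.5 to 2.5 m/s for moderate, and 1.5 m/s or less for large.
- Two rows grade end-diastolic flow: "Decreased or absent end-diastolic flow in DA" for moderate and "Reversed end-diastolic flow in the DA" for large.

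Where Section 6.0 lists the echocardiographic data to be collected, the duct's own measurements are called "PDA size, PDA flow direction".

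Table 1 is an operative rule. Sections 6.0 and 10.0 use it to decide whether an infant has a hemodynamically significant PDA. Both sets of rescue criteria in Section 6.0 count its large echocardiographic criteria.

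**The concern.** One printed definition has to serve five rows, and it appears to be right for two and wrong for three. Reduced, absent or reversed end-diastolic flow is a sensible descending-aorta measurement when a duct draws blood away in diastole. A peak velocity that is high when the duct is narrow and low when it is wide describes flow through the duct itself.

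A reader who followed the footnote would sample the descending aorta for the velocity item. That item could then be scored moderate or large whatever the size of the duct. It is one of the large criteria that count towards rescue. Two sites obtain the studies, and Section 6.0 has the second site analyze its own under its institutional protocol, so the table wording is what the sites have in common. The pilot is meant to feed a larger multi-site trial, and an uncorrected table could be carried into it.

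**Working it through.** The plan gives no figure to reproduce here. The check sets the rows against the footnote and then tests the aortic reading for plausibility.

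**1. Count the uses of DA (Table 1).** Velocity rows: small, moderate, large = 3. End-diastolic-flow rows: moderate, large = 2. Total 3 + 2 = 5.

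**2. Compare the velocity bands with the duct diameters beside them (Table 1).** Gradients use the simplified Bernoulli relation, gradient = 4v² (v in m/s, result in mm Hg). This is an assumed standard formula that the protocol does not state. The cut-points give 4 × 2.5² = 25 and 4 × 1.5² = 9.

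| Grade | Duct diameter | Vmax | Gradient, 4v² |
|---|---|---|---|
| Small | <1.5 mm | >2.5 m/s | >25 mm Hg |
| Moderate | 1.5–3 mm | 1.5–2.5 m/s | 9–25 mm Hg |
| Large | ≥3 mm | ≤1.5 m/s | ≤9 mm Hg |

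Velocity falls as diameter rises, which is the pattern of a restrictive versus a wide-open duct.

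**3. Test the aortic reading against the protocol's own threshold.** When the left pulmonary artery and descending aorta are checked before device release, Section 6.0 treats a maximal instantaneous gradient above 15 mm Hg as stenosis. The matching velocity is √(15/4) = 1.94 m/s. If Vmax were aortic:

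- The small grade would need more than 25 mm Hg, which exceeds 15 mm Hg, although Section 10.0 excludes infants with evidence of coarctation.
- An aorta without stenosis by that threshold would have a velocity of at most 1.94 m/s. It would be scored moderate or large, and never small, regardless of the duct.

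**4. Weight of the item.** Taking LVEDD as part of the LA:Ao item, the large criteria are diameter, Vmax, LA:Ao ratio, left ventricular output and end-diastolic flow. Vmax is therefore 1 of 5 large criteria. It is also 1 of 5 moderate and 1 of 4 small criteria.

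**5. Consequence at rescue.** Rescue Criteria #2 needs at least 1 large criterion. If an aortic value of 1.5 m/s or less were scored large, 1 − 1 = 0 of the other 4 would be needed. Mitral regurgitation, moderate or severe clinical criteria and a judgement of medical necessity would still be required. This example is hypothetical, and how often it would arise is unknown.

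**6. Ceiling on exposure (Section 12.0).** The rescue rule applies to 10 + 10 = 20 planned conservative-arm infants. The entry table applies to at least the 20 + 20 = 40 planned randomized infants. These are enrolment targets, not estimates of infants affected.

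**The case against.** The strongest reply is that this is an ambiguous abbreviation and not a wrong measurement rule. In a table about the PDA, directly below duct diameter, a cardiologist would probably read the velocity item as ductus arteriosus flow, and the protocol does use the words ductus and ductal elsewhere. No section says where Vmax is sampled, so the ductal reading is an inference from physiology. The numerical check needs a formula from outside the documents, and the 15 mm Hg threshold is a device-release rule, not an eligibility rule. Entry also requires verification by the treating cardiologist. Neither Section 6.0, Section 10.0 nor Table 1 says how many echocardiographic items must be met at entry, so a misread item cannot be shown to change any infant's eligibility.

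Most of this stands, and it is why the point is minor. It does not remove the error. The footnote does not leave DA undefined. It gives a meaning, and using the three velocity rows correctly depends on the reader ignoring it. The inverse grading and the stenosis comparison both point to the duct, and nothing in the protocol points to an aortic velocity.

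**Conclusion.** The concern holds as a minor labelling error in an operative table: the printed meaning of DA fits two of its five uses and not the other three. If followed literally, one of the five large criteria would be measured in the wrong vessel. The probable effect is small, and the documents do not allow it to be sized. No sample size, endpoint or analysis is affected, and the velocity item never triggers rescue alone.

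Confidence is medium. The conclusion rests on reading the inverse velocity grading as ductal flow, on 4v² for the gradients, and on carrying the device-release stenosis threshold over as a plausibility check. The documents give no normal aortic velocities.

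**What to change.** After confirmation by the clinical leads, relabel the three velocity rows of Table 1 as PDA (ductal) flow Vmax, using the abbreviation Section 1.0 already defines. Keep DA as descending aorta for the two end-diastolic-flow rows. Redefining DA as ductus arteriosus throughout would only move the error to those two rows. Issue the same wording to both sites.

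The cost is three row labels in one table, with no added measurement and no change to any cut-point.
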